9.3.2. Unsolicited Adverse Events

When calculating the incidence of unsolicited AEs (i.e., on a per subject basis), each subject will only be counted once at the highest severity and/or relationship, and any repetitions of AEs within a subject will be

ignored; the denominator will be the total number of subjects in the safety population. All AEs reported will be included in the summaries and analyses.

A summary of all unsolicited adverse events by MedDRA SOC, PT, and study arm that occurred from Day 1 to Day 365 is provided in [Table 124](#). Similarly, a summary of all unsolicited adverse events by MedDRA SOC, PT, and study arm that occurred from Day 1 to Day 29 is provided in [Table 125](#).

The number and percentage of subjects reporting at least one unsolicited AE will be summarized by MedDRA system organ class and preferred term. A 95% CI will be presented for the percentage of subjects reporting any unsolicited AE (serious or non-serious) for each MedDRA system organ class and preferred term over all study vaccinations ([Table 126](#)). A similar table summarizing all unsolicited events from Day 1 to Day 29 will be provided ([Table 127](#)).

The following summaries for unsolicited AEs will be presented by MedDRA system organ class, preferred term, and study arm:

- Incidence of AEs by severity and relationship to study product ([Table 128](#));
- Incidence of AEs from Day 1 to Day 29 by severity and relationship to study product ([Table 129](#));
- Incidence of non-serious, related AEs by severity ([Table 130](#));
- Incidence of AEs over time (Days 1-8, Days 9-29 post first study vaccination) ([Table 131](#));
- Incidence of non-serious, related AEs over time (Days 1-8, Days 9-29 post first study vaccination) ([Table 132](#));
- Total frequency of AEs over time (Days 1-8, Days 9-29 post first study vaccination) ([Table 133](#));
- Subject listing of non-serious AEs of moderate or greater severity ([Table 138](#));
- Bar chart displaying total frequency of AEs by severity and MedDRA system organ class and study arm ([Figure 98](#));
- Bar chart displaying incidence of AEs by severity and MedDRA system organ class, and study arm ([Figure 99](#));
- Bar chart displaying total frequency and incidence of AEs by relationship to study product, MedDRA system organ class, and study arm ([Figure 100](#) and [Figure 101](#)).

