It is anticipated that both adjuvant formulations (AF03 and Advax-CpG55.2) will be available at the start of study enrollment. However, if the Advax-CpG55.2 is not available, the study will proceed only with groups 1, 2, 4 and 5 open for enrollment for the remaining subjects (up to 240, 60 per group). For the sentinel subjects, one subject from groups 1, 2, 4 and 5 will be enrolled and followed through Day 8. If any of the pre-specified halting rules occur, the study will be halted and reviewed by the DSMB. If no pre-specified events occur, randomization will proceed in groups 1, 2, 4 and 5 for the remaining subjects.

The DSMB will review the data when the 8-day reactogenicity and clinical safety laboratory data following the first study vaccination is available for 50% of study subjects. Enrollment will not be paused for this review. An additional scheduled DSMB review will occur when all HAI, NAI and Neut data for Day 1, and Day 29 and safety data through Day 57 following the first study vaccination, are available.

Reactogenicity will be measured by the occurrence of solicited injection site and systemic reactions from the time of the first study vaccination through Day 8. Unsolicited non-serious adverse events (AEs) will be collected from Day 1 through approximately Day 29. Serious adverse events (SAEs), AESIs including reports of tearing, dry mouth, dry eyes and MAAEs, including NOCMCs and PIMMCs, will be collected through approximately 12 months after the first study vaccination. Clinical safety laboratory evaluations (hematology and chemistry) will be performed at screening, immediately prior to the first study vaccination and approximately Day 8.

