## **7 STUDY PROCEDURES/EVALUATIONS**

### **7.1 Clinical Evaluations**

A complete medical history will be obtained by interview of subjects at the screening visit. Subjects will be queried regarding a history of significant medical disorders of the head, eyes, ears, nose, throat, mouth, cardiovascular system, lungs, gastrointestinal tract, liver, pancreas, kidney, urologic system, nervous system, blood, lymph nodes, endocrine system, musculoskeletal system, skin, and genital/reproductive tract. A history of any allergies, cancer, immunodeficiency, psychiatric illness, substance abuse, and autoimmune disease will be solicited. At all subsequent visits an interim medical history will be obtained by interview of subjects and any changes since the previous clinic visit or phone call will be noted. The interim medical history should include an assessment for new medical conditions and symptoms suggestive of AESIs (including Protocol Specified AESIs, MAAEs, NOCMCs and PIMMCs).

Concomitant medications and influenza vaccination history will be collected as described in [Section 6.5](#).

At the screening visit a physical examination will be performed on all subjects, by a study clinician licensed to make medical diagnoses and listed on the Form FDA 1572 as the site PI or sub-investigator, to include the following organs and organ systems: skin, head and neck, lungs, heart, liver, spleen, extremities, lymph nodes, and nervous system.. At the vaccination visit and at follow-up visits after each study vaccination, a targeted physical examination may be performed, if indicated based on the subject's interim medical history, by a study clinician licensed to make medical diagnoses and listed on the Form FDA 1572 as the site PI or sub-investigator. Targeted physical examinations should also include an assessment for signs suggestive of PIMMCs.

Height, weight will be collected at the screening visit, and vital signs (oral temperature, pulse and blood pressure) will be collected at the screening visit and prior to the first study vaccination. Vital signs assessed on Day 1 prior to the first study vaccination will be considered as baseline. Subjects must not eat or drink anything hot or cold, or smoke within 10 minutes prior to taking oral temperature.

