### **8.2.7 Visit 08, Day 180, Clinic Visit**

**(Window: Day 180+/- 14d)**

- Interim medical history, including an assessment for new medical conditions, stability of chronic diseases and symptoms suggestive of AESIs (including Protocol Specified AESIs, MAAEs, NOCMCs and PIMMCs), will be obtained by interview of subjects and any changes since the previous clinic visit will be noted.
- Receipt of any non-study influenza vaccines will be recorded on the appropriate DCF.
- Only SAEs and AESIs (including Protocol Specified AESIs, MAAEs, NOCMCs and PIMMCs), will be recorded on the appropriate DCF.
- A targeted physical examination, including an assessment for signs suggestive of AESIs (including Protocol Specified AESIs, MAAEs, NOCMCs and PIMMCs) may be performed, if indicated based on review of interim medical history, by a study clinician licensed to make medical diagnoses and listed on the Form FDA 1572 as the site PI or sub-investigator.
- Approximately 20 mL of venous blood will be collected for serological assays.

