## **9 ASSESSMENT OF SAFETY**

### **9.1 Specification of Safety Parameters**

Safety will be assessed by the frequency and severity of:

1. SAEs occurring from the time of the first study vaccination through approximately 12 months after the first study vaccination.
2. Solicited AEs – reactogenicity events occurring from the time of the first study vaccination through 7 days after the first study vaccination:
  - a) Injection site reactions including pruritus, ecchymosis, erythema, induration, edema, pain, and tenderness.
  - b) Systemic reactions including fever, feverishness, fatigue, malaise, myalgia, arthralgia, headache, and nausea.
3. Clinical safety laboratory AEs occurring from the time of the first study vaccination through approximately 7 days after the first study vaccination. Parameters to be evaluated include WBC, Hgb, PLT, ALT, T. Bili, AST, GGT, ALP, serum lipase, serum amylase, and Cr.
4. Unsolicited AEs –non-serious AEs occurring from the time of the first study vaccination through approximately Day 29.
5. AESIs (including Protocol Specified AESIs, MAAEs, NOCMCs and PIMMCs) occurring from the time of the study vaccination through approximately 12 months after the first study vaccination.

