14.3.6 Displays of Vital Signs

Table 164: Vital Signs by Assessment, Maximum Severity, Time Point, and Study Arm – Any Assessment

Study Arm	Study Day	N	None		Mild		Moderate		Severe		Missing	
			n	%	n	%	n	%	n	%	n	%
Group 1: Fluzone (N=X)	Baseline	x	x	xx	x	xx	x	xx	x	xx	x	xx
	Max Severity Post Baseline	x	x	xx	x	xx	x	xx	x	xx	x	xx
Group 2: Fluzone + AF03 (N=X)	Baseline	x	x	xx	x	xx	x	xx	x	xx	x	xx
	Max Severity Post Baseline	x	x	xx	x	xx	x	xx	x	xx	x	xx
Group 3: Fluzone + Advax-CpG (N=X)	Baseline	x	x	xx	x	xx	x	xx	x	xx	x	xx
	Max Severity Post Baseline	x	x	xx	x	xx	x	xx	x	xx	x	xx
Group 4: Flublok (N=X)	Baseline	x	x	xx	x	xx	x	xx	x	xx	x	xx
	Max Severity Post Baseline	x	x	xx	x	xx	x	xx	x	xx	x	xx
Group 5: Flublok + AF03 (N=X)	Baseline	x	x	xx	x	xx	x	xx	x	xx	x	xx
	Max Severity Post Baseline	x	x	xx	x	xx	x	xx	x	xx	x	xx
Group 6: Flublok + Advax-CpG (N=X)	Baseline	x	x	xx	x	xx	x	xx	x	xx	x	xx
	Max Severity Post Baseline	x	x	xx	x	xx	x	xx	x	xx	x	xx

Note: The “Max Post Baseline” rows indicate the maximum severity experienced by each subject at any time point post baseline, including unscheduled assessments.
N= Number of subjects in the Safety Population

Table with similar format

Table 165: Vital Signs by Assessment, Maximum Severity, Time Point, and Study Arm – Oral Temperature

Table 166: Vital Signs by Assessment, Maximum Severity, Study Day, and Study Arm – Systolic Blood Pressure

Study Arm	Study Day	N	None		Mild (Low)		Mild (High)		Moderate (Low)		Moderate (High)		Severe (Low)		Severe (High)		Missing	
			n	%	n	%	n	%	n	%	n	%	n	%	n	%	n	%
			Group 1: Fluzone (N=X)	Baseline	x	x	xx	x	xx	x	xx	x	xx	x	xx	x	xx	x
	Max Severity Post Baseline	x	x	xx	x	xx	x	xx	x	xx	x	xx	x	xx	x	xx	x	xx
Group 2: Fluzone + AF03 (N=X)	Baseline	x	x	xx	x	xx	x	xx	x	xx	x	xx	x	xx	x	xx	x	xx
	Max Severity Post Baseline	x	x	xx	x	xx	x	xx	x	xx	x	xx	x	xx	x	xx	x	xx
Group 3: Fluzone + Advax-CpG (N=X)	Baseline	x	x	xx	x	xx	x	xx	x	xx	x	xx	x	xx	x	xx	x	xx
	Max Severity Post Baseline	x	x	xx	x	xx	x	xx	x	xx	x	xx	x	xx	x	xx	x	xx
Group 4: Flublok (N=X)	Baseline	x	x	xx	x	xx	x	xx	x	xx	x	xx	x	xx	x	xx	x	xx
	Max Severity Post Baseline	x	x	xx	x	xx	x	xx	x	xx	x	xx	x	xx	x	xx	x	xx
Group 5: Flublok + AF03 (N=X)	Baseline	x	x	xx	x	xx	x	xx	x	xx	x	xx	x	xx	x	xx	x	xx
	Max Severity Post Baseline	x	x	xx	x	xx	x	xx	x	xx	x	xx	x	xx	x	xx	x	xx
Group 6: Flublok + Advax-CpG (N=X)	Baseline	x	x	xx	x	xx	x	xx	x	xx	x	xx	x	xx	x	xx	x	xx
	Max Severity Post Baseline	x	x	xx	x	xx	x	xx	x	xx	x	xx	x	xx	x	xx	x	xx

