14.3.1.2 Unsolicited Adverse Events

Figure 98: Frequency of Unsolicited Adverse Events by MedDRA System Organ Class and Severity

[Implementation Note: A Generic figure is shown below. This figure includes all unsolicited events across all doses. A horizontal bar chart should be presented in 1 image file separate panels for each study arm (6 panels: Top row: Groups 1, 2, 3; Bottom row: Groups 4, 5, 6). Axes should be labeled as follows: y-axis label: System Organ Class, y-axis label: Number of Events. The study arms should be indicated in the panel headers including “(N=X)”, where N = the number of subjects in the in the Safety Population. The y-axis should present all SOCs reported by at least 1 subject and an “All Events” category. Y-axis should be sorted with “All Events first, then in decreasing order of total incidence]

[figure not shown]

Figure 99: Incidence of Unsolicited Adverse Events by MedDRA System Organ Class and Maximum Severity

[Implementation Note: A Generic figure is shown below. This figure includes all unsolicited events across all doses. A horizontal bar chart should be presented in 1 image file with separate panels for each study arm (6 panels: Top row: Groups 1, 2, 3; Bottom row: Groups 4, 5, 6). Axes should be labeled as follows: y-axis label: System Organ Class, x-axis label: Percentage of Subjects (%). The study arms should be indicated in the panel headers including “(N=X)”, where N = the number of subjects in the in the Safety Population. Subjects are counted at most once at the maximum severity across for any events in the applicable SOC. The y-axis should present all SOCs reported by at least 1 subject and an “All Events” category. Y-axis should be sorted with “All Events” first then in decreasing order of total incidence]

[figure not shown]

Figure 100: Frequency of Adverse Events by MedDRA System Organ Class and Relationship to Treatment

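### After Day 29 only SAEs and AESIs are collected, so the SAP's Day 1–365, all-dose and open-ended unsolicited-AE outputs mix full with filtered capture; the post-baseline vital-sign rows have no scheduled data behind them

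*SAP*

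**What the plan says.** **What is collected.** Protocol section 4 states: "Unsolicited non-serious adverse events (AEs) will be collected from Day 1 through approximately Day 29". Protocol section 9.1 repeats the limit ("Unsolicited AEs –non-serious AEs occurring from the time of the first study vaccination through approximately Day 29"), and SAP section 4.5.1 defines the variable in the same way. Footnote 3 to the schedule in Protocol Appendix A ties general AE recording to visits on or before Day 29. For the Day 180 visit, Protocol section 8.2.7 says: "Only SAEs and AESIs (including Protocol Specified AESIs, MAAEs, NOCMCs and PIMMCs), will be recorded on the appropriate DCF". Visits 05, 06, 07 and 09 list the same classes. Under Protocol section 9.2.1 an AESI may be serious or not, and an MAAE is defined by unscheduled medical care, not by seriousness. Section 9.3 carries these classes, with SAEs, to about 12 months.

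**What is reported.** SAP section 9.3.2 describes Table 124 as "A summary of all unsolicited adverse events by MedDRA SOC, PT, and study arm that occurred from Day 1 to Day 365". It asks for 95% CIs in Table 126 "for each MedDRA system organ class and preferred term over all study vaccinations", covering serious and non-serious events. Tables 128 and 130 state no period. The notes to Figures 98–101 each say: "This figure includes all unsolicited events across all doses". The denominator is the whole Safety Population. Tables 125, 127 and 129 repeat Tables 124, 126 and 128 for Days 1–29, and Tables 131–133 are also confined to Days 1–29.

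**Vital signs.** Protocol section 7.1 says "vital signs (oral temperature, pulse and blood pressure) will be collected at the screening visit and prior to the first study vaccination". SAP section 9.7 likewise places the assessment before vaccination on Day 1. Tables 164–168 nevertheless carry a post-baseline maximum-severity row for every arm. Their note explains that these "rows indicate the maximum severity experienced by each subject at any time point post baseline, including unscheduled assessments".

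**The concern.** The reporting windows are wider than the collection window, and the SAP sets no boundary between them in these outputs. Up to about Day 29 every unsolicited AE is sought. After that, an event enters the database only if it is an SAE or falls in an AESI class. A mild event for which no care was sought counts on Day 20 and does not count on Day 100, yet both days sit under the same heading and the same denominator. A subject whose later event was never recorded is treated as event-free.

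Two quantities are affected: the absolute 12-month or all-dose incidence with its CI, and the severity mix, because the later events have passed a filter that favours events needing care. Dose 2 falls wholly inside the filtered phase when given in its window, so an all-dose figure carries no general AE experience after that dose.

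The vital-sign rows have a similar problem. The shells provide a post-baseline result for each arm, but the schedule produces no such measurement.

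**Working it through.** The documents give no figure to reproduce. The check sets collection windows against reporting windows and counts days.

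**Outputs against windows**

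| SAP output | Content | Period or doses named | Matching Day 1–29 output |
|---|---|---|---|
| Table 124 | SAEs, and all unsolicited AEs | Days 1–365 | Table 125 |
| Table 126 | Any unsolicited AE, 95% CI | All study vaccinations | Table 127 |
| Table 128 | Severity and relationship | None stated | Table 129 |
| Table 130 | Related non-serious AEs by severity | None stated | None by severity (Table 132 is by time period) |
| Figures 98–101 | Counts and incidence by SOC | All doses | None |

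**Day counts**

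- General collection: 29/365 = 7.9%. With the Visit 04 window of ±2 days: 27/365 = 7.4% to 31/365 = 8.5%.
- Filtered collection: 365 − 29 = 336 days, and 336/365 = 92.1%.
- From Day 29 to dose 2: 90 − 29 = 61 days. Over the Day 76–104 window: 76 − 29 = 47 to 104 − 29 = 75. Protocol section 8.5 also lets sites give dose 2 before Day 76 when local influenza activity is high, which would shorten the gap for those subjects.
- From dose 2 to Day 365 inclusive: 365 − 90 + 1 = 276 days (262 to 290 over the window). General non-serious AE collection covers 0 of them. At Visit 06 no general AE collection restarts.
- Table 130 is starred for the Expedited Report, which uses safety data through Day 57. There the mixture is 29 days of full capture and 57 − 29 = 28 days of filtered capture.

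**Direction.** Each subject counts once, so the Table 126 percentage cannot be below the Table 127 percentage. It also cannot exceed what full collection over the year would have given. It lies between two interpretable quantities and equals neither by design. The distance cannot be computed, because the documents give neither the background AE rate nor the share of events that meet an SAE or AESI definition.

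**Vital signs.** In the Appendix A schedule the vital-sign row is marked at V00 and V01 (before dosing), blank at V02–V09, and marked again for early-termination and unscheduled visits. Scheduled post-dose clinic assessments: 0 of 8 follow-up visits. Protocol sections 8.4 and 8.5 make the remaining readings optional, if indicated.

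**The case against.** The strongest defence is that the primary safety outcome, unsolicited AEs through about Day 29, is reported cleanly. Three of the four tables have Day 1–29 companions, SAP sections 4.1 and 4.5.1 state the collection windows, and Table 124 separates SAEs from unsolicited AEs. The percentages are arithmetically right for events reported. The rule is identical in all six arms. The wider tables also tabulate post-Day-29 MAAEs and other AESIs, which belong to the 12-month secondary safety outcome. Tables 164–168 have a column for missing values and say that unscheduled readings are included, so their sparsity would show.

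Most of this stands, and it limits the point. It does not remove it. Being right for events reported is not the same as being right for the period and doses in the title, and no planned footnote tells the reader. Table 130 by severity and Figures 98–101 have no Day 1–29 counterpart. The change is also undeclared. Protocol section 11.6.2 lists SAEs and AESIs and tabulates non-serious unsolicited AEs separately, while SAP section 12 does not mention pooling to Day 365.

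Several stronger readings are tempting, and the documents do not support them:

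- *No non-serious AE is collected after Day 29 or after dose 2.* Not so: non-serious AESIs, including MAAEs, NOCMCs and PIMMCs, are collected to about 12 months.
- *Arm comparisons are biased.* The collection rule is the same in every arm, so it gives no ground for this.
- *The tables will be read as showing a low AE rate over the year.* That is conjecture, and the cumulative figure cannot fall below its Day 1–29 companion.
- *Post-baseline vital signs come only from subjects who left or were unwell.* Protocol section 8.5 allows an unscheduled visit at any time, and its listed activities include early seasonal vaccination.
- *Post-dose temperature is missing.* Subjects record it daily on the Memory Aid through Day 8, and it is graded as solicited fever.

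**Conclusion.** The point holds as a defect of labelling and interpretation. For 336 of the 365 days named (92.1%), and for all time after dose 2 when it is given in its window, Tables 124, 126, 128 and 130 and Figures 98–101 rest on SAE and AESI capture only, pooled with full capture before Day 29. Their absolute rates, CIs and severity mix therefore do not describe the period and doses named. The Day 1–29 results in Tables 125, 127 and 129 are sound. The practical weight falls on Table 130, which also enters the Expedited Report, and on Figures 98–101.

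The post-baseline rows in Tables 164–168 will be mostly empty and filled only by optional readings. They cannot describe post-vaccination pulse or blood pressure by arm.

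This rests on sites following the schedule, so that other non-serious AEs are not recorded after about Day 29. Sample size, power and type I error are unaffected. The correction should be made, but nothing in the conduct of the trial depends on it.

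**What to change.** 1. **Table 130 and Figures 98–101:** present all unsolicited AEs with onset on Days 1–29 after dose 1, and say so in the titles. Move later events from Table 130 to the tabulation in item 2.
2. **Tables 124, 126 and 128:** keep the post-Day-29 data, but show them separately by SOC and PT as SAEs and as AESIs, MAAEs, NOCMCs and PIMMCs, with the collection rule in a footnote. Simply restricting Tables 126 and 128 to Days 1–29 would duplicate 127 and 129 and lose this tabulation. SAP section 9.4 plans no separate MAAE listing.
3. **Wording:** where later data are included, remove the descriptions that claim all unsolicited events, all study vaccinations or all doses, from SAP section 9.3.2, the shells and the figure notes.
4. **Tables 164–168:** drop the post-baseline maximum-severity rows, or replace them with a listing labelled as unscheduled or early-termination values only.
5. **SAP section 12:** record the change.

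The cost is SAP text, table shells and programming. The Day 1–29 layouts already exist for three of the tables, and no new data are needed. Adding pulse and blood-pressure readings after dosing is not proposed. It would be a new procedure, and the Table 14 shell already carries first-vaccination dates of 17 June to 27 August 2019, so it appears too late.

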9.4. Deaths, Serious Adverse Events and other Significant Adverse Events

The following listings will be presented including Subject ID, Age (years) AE Description, AE Onset Date/End Date, Last Vaccination Received/Days Post Vaccination, Reason Reported as an SAE, Relationship to Study Product, Alternate Etiology if not Related, Outcome, and Duration of Event (days):

- Deaths and Serious Adverse Events ([Table 134](#));
- Adverse Events of Special Interest ([Table 135](#));
- Potentially Immune Mediated Medical Conditions ([Table 136](#));

- New Onset Chronic Medical Conditions ([Table 137](#)).

A listing of all reported AEs by subject will be presented in [Listing 22](#), sorted by Study Arm, Subject ID, and AE Number.

9.5. Pregnancies

For any subjects in the Safety Population who became pregnant during the study, every attempt will be made to follow these subjects to completion of pregnancy to document the outcome, including information regarding any complications with pregnancy and/or delivery.

[Listing 28](#), [Listing 29](#), [Listing 30](#), [Listing 31](#), and [Listing 32](#) will present any study pregnancies and their outcomes.

